### **Sample Size/Feasibility**

Our sample size calculation is based on the assumption that a 25% relative risk reduction can be achieved with the intervention, i.e. a drop from 32% to 24%. Based on APHP data from 2009 to 2014, we have estimated the intra-cluster correlation (after adjustment for prior 5 year rate) as .002, but to be conservative we have assumed an ICC of .01 (well above the upper 95% confidence limit). Using the conventional adjustment for clusters, yields a requirement for 26 centres to provide at least 80% power at the usual (two-sided) 5% significance level. Simulations based on the observed 2014 instances of primipara birth in the 26 participating hospitals show that we have power exceeding 80% to detect even a 10% relative risk reduction.

### **Data Collection**

The Alberta Perinatal Health Program (APHP) collects perinatal data from the provincial delivery record for all hospital births in Alberta. Data from the delivery records is validated through detailed computer programming that double checks all variables. All the stillbirths or neonatal deaths are captured by APHP.

APHP data is validated with Alberta Vital Statistics data for all deaths. Data is available for a number of variables ie: maternal demographics, type of labor, duration of labor, route of delivery, cervical dilation prior to CS, Apgars, neonatal resuscitation, cord blood gasses, post partum hemorrhage, maternal transfusion, and neonatal admission to NICU. Information is available for individual sites and practitioners. To assess neonatal outcomes such as asphyxia, data will be obtained from the Edmonton and Calgary site data of the Canadian Neonatal Network (CNN). Neonatal outcomes will include: intrapartum stillbirth, neonatal death, 5 minute Apgar score<7, cord pH<7.0 with base excess <12 mmol/l, moderate or severe asphyxia (Sarnat criteria) and therapeutic cooling. The evaluation of the neonatal outcomes will in collaboration with an emerging surveillance program which is monitoring the rate of neonatal asphyxia in Alberta. The data abstractors for the APHP and CNN will not be involved in the trial and will be unaware of site allocation. The data will be provided as in-kind support by the APHP. Given that data on at least 22,000 subjects will be provided this is an in-kind support equivalent to approximately 4 million dollars.

We will review the obstetrical charts of stillbirth cases from Jan 2018 to Feb 2020 to determine if the stillbirth occurred during the antenatal or intrapartum period. Chart review of stillbirth cases prior to Jan 2018 will be completed by APHP as part of their data validation process.

We will use a previously validated labor culture survey to assess differences in unit culture between sites and to see if these differences may explain the variable uptake of the guidelines. The labor culture survey has six subscales that include the following: best practices to reduce cesarean delivery, cesarean safety, fear of vaginal birth, maternal agency, physician oversight and unit microculture. The survey will also include questions related to participant and unit engagement with the REDUCED guidelines.

The labor culture survey will be an online survey, which will be emailed to physicians and nursing staff at intervention sites in fall 2019. The survey will be administered by Research Electronic Data Capture (REDCap), which is a secure, browser-based application designed to support electronic data capture. The Clinical Research Unit (CRU) in the Faculty of Medicine at the University of Calgary is the REDCap host.

**[April 27, 2020 update: Due to possible effects of the COVID-19 pandemic on the trial, an urgent steering committee meeting was convened on April 24, 2020. The decision was made to terminate the study as of February 29, 2020 (i.e., prior to the World Health Organization [WHO] declaring COVID-19 a global pandemic on March 11, 2020), instead of Phase I ending on November 30, 2019 and Phase 2 ending on November 30, 2021. This decision was made prior to the study team receiving the final data for the trial. The official statement of the steering committee regarding the end of the REDUCED Trial due to the pandemic can be found in Appendix 1. The dates in this version of the protocol reflect the new end date of the trial of February 29, 2020, and changes are bolded].**

Data collection will include retrospective (baseline) data for the two years prior to the roll out of the intervention (2015 and 2016) and will continue until 27 months after the completion of implementation for all sites (**February 29, 2020**). Intervention and post-intervention periods will be defined for intervention sites according to their dates of initiation and completion of implementation.

A random sample of obstetrical charts will be reviewed from the 13 intervention sites during the **27 month** period from Dec 1, 2017 to **February 29, 2020** to determine the percentage of cesarean sections for dystocia that were done following the ACOG/SMFM guidelines. A minimum of 50 charts per site will be reviewed. If there are fewer than 50 cesarean sections for dystocia at a given site, then all of the dystocia cases during the two-year period will be reviewed.

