## TABLE OF REVISIONS

Version	Date of revision	Comments
1	May 31, 2017	- Original protocol
2	Sept 8, 2018	
 
- Clarified that our study population includes primiparous women “at term (<math>\geq 37</math> weeks), with a vertex presenting singleton fetus”
 
- Provided an updated definition for neonatal asphyxia
 
- Updated this paragraph of the statistical analysis: “The intervention period for the study will be taken as starting with the first day of roll-out (initiation complete at that site) of the guidelines until the completion of the program at all sites, with baseline and post-intervention encompassing the two year and four year periods before and after. The primary analysis will be performed on data for the period of time from completion of all site initiation (December 1 2017, until a 2 year period has expired from the initiation of the final intervention site (November 30th 2019). A subsequent 4 year analysis is also planned for data up to November 30th 2021. Occurrence of CS will be assessed over baseline and post-intervention using a repeated mixed effects logistic regression model following a constrained baseline approach which confines group differences to the post-intervention period, assuming no systematic difference during the baseline period. The random effects will include site and period within site. Having fewer than 40 sites, a small sample correction will be applied to the standard error for group differences underlying significance tests and confidence interval construction. As a secondary analysis, we will include data from the intervention period reflecting the site-specific dates for completion of the intervention (1st site completed initiation Feb 1 2017), incorporating a linear time trend to accommodate the potential for confounding of an underlying secular trend.”
 

3	April 25, 2019	
 
- Added labour culture survey methodology.
 
- Added three secondary outcomes, including: postpartum uterine artery/pelvic artery embolization; postpartum hysterectomy; and postpartum maternal intensive care unit (ICU) admission.
 
- Added this statement to the statistical analysis: “The model will include year and treatment plus treatment by year interaction over the intervention period, with corresponding random effects by site”.
 

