**Secondary outcomes: Adverse neonatal and maternal outcomes including:**

Neonatal:

- a) Perinatal death;
- b) Neonatal Asphyxia: intrapartum stillbirth or neonatal death from asphyxia (Perinatal Society of Australia and New Zealand coding) or Neonatal Intensive Care Unit admission and at least two of: a. Apgar score of  $\leq 5$  at 10 minutes; b. Mechanical ventilation or chest compressions for resuscitation within 10 minutes; c. Cord pH  $< 7.00$  (venous or arterial), or arterial base excess  $\geq 12$  at birth;
- c) moderate or severe asphyxia or meets criteria for therapeutic cooling; and
- d) sepsis or suspected sepsis.

Maternal:

- a) post partum hemorrhage;
- b) blood transfusion;
- c) postpartum uterine artery/pelvic artery embolization;
- d) postpartum hysterectomy; and
- e) postpartum maternal intensive care unit (ICU) admission.

**Other secondary outcomes:** overall CS rate in primiparous women, overall cesarean section rate, rate of successful trial of labor, induction rate, augmentation of labor rate, duration of labor, and cervical dilation prior to cesarean section.

**Implementation outcomes:** Implementation quality (80% provider education completion pre-trial), site responsiveness (attendance and website tool access rates, attendance at feedback sessions by profession, frequency of coaching access), guideline adherence (adherence rate by site), and adaptation (implementation toolkit element use by site). Qualitative process and summative outcomes will capture how and why implementation was executed, by site, explore intrapartum and site leader perceptions of implementation, gather feedback on the implementation toolkit elements and utility.

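### The base-excess cut-off of 12 points in opposite directions in Secondary outcomes and Data Collection, and no sign convention says which scale is meant

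*Combined protocol and SAP*

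**What the plan says.** Secondary outcomes defines neonatal asphyxia by two routes. One is an asphyxial death. The other is "Neonatal Intensive Care Unit admission and at least two of" three criteria: (a) a low 10-minute Apgar score, (b) early ventilation or chest compressions, and (c) a cord-gas criterion. Criterion c is met by cord pH below 7.00 ("venous or arterial), or arterial base excess" at or above 12). It gives no unit for base excess. The same list carries perinatal death and "moderate or severe asphyxia or meets criteria for therapeutic cooling" as separate outcomes.

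Data Collection returns to the subject with "Neonatal outcomes will include: intrapartum stillbirth, neonatal death" and then includes the items "5 minute Apgar score<7, cord pH<7.0 with base excess <12 mmol/l". The second of these gives a unit but names no vessel.

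Neither section prints a minus sign, uses the term base deficit or states a sign convention. Data Collection names "neonatal resuscitation, cord blood gasses, post partum hemorrhage" among the variables available from the provincial perinatal data, without describing how base excess is stored. The Table of Revisions records, for Version 2, "Provided an updated definition for neonatal asphyxia"; nothing says whether the Data Collection wording predates that change.

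**The concern.** The same quantity and the same number appear with opposite inequalities. A programmer who follows either section literally needs to know whether a sick infant's value is stored as, say, −16 or 16, and the documents do not say. Depending on the answer, a cord-gas rule can stop discriminating or can discriminate the wrong way.

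The stake is the definition of a neonatal safety outcome. The study question asks about cesarean rates subject to no increase in maternal or neonatal morbidity, and Background acknowledges that the guidelines lengthen fetal exposure to labor. The revised Phase 2 extends the post-intervention period, to 28 February 2025 at the latest, so the definition should also be the same across analyses.

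**Working it through.** There is no planned figure to reproduce. The check is to apply each rule as printed on both possible scales.

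Inputs from the documents: criterion c is pH < 7.00 or base excess ≥ 12 (Secondary outcomes); the listed item is pH < 7.0 and base excess < 12 (Data Collection).

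Assumptions, not stated in the documents: metabolic acidosis is negative on the signed scale (deficit = −base excess), and the intended criterion is a deficit of 12 or more. The pH and base-excess values below are illustrative.

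| Infant | pH | Signed value | Deficit | Data Collection item: intended | as printed, signed | as printed, deficit | Criterion c: intended | as printed, signed | as printed, deficit |
|---|---|---|---|---|---|---|---|---|---|
| A | 6.9 | −16 | 16 | yes | yes | no | yes | yes | yes |
| B | 6.9 | −8 | 8 | no | yes | yes | yes | yes | yes |
| C | 7.1 | −16 | 16 | no | no | no | yes | no | yes |
| D | 7.1 | −8 | 8 | no | no | no | no | no | no |

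*Data Collection item, signed scale.* −16 < 12 and −8 < 12 are both true, so the base-excess condition excludes no acidotic infant and the item becomes pH < 7.0. It keeps A, correctly, and adds B.

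*Data Collection item, deficit scale.* 16 < 12 is false and 8 < 12 is true. The item drops A, the intended case, and counts B.

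*Criterion c, deficit scale.* 16 ≥ 12 is true and 8 ≥ 12 is false. All four infants are classified as intended.

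*Criterion c, signed scale, coded literally.* −16 ≥ 12 is false, so the base-excess limb never fires for an acidotic infant and C is missed.

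So on a signed scale both rules lose their base-excess condition, and on a deficit scale the Data Collection rule is reversed. No single scale makes both work.

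*Effect on the asphyxia composite.* Among NICU-admitted infants without asphyxial death there are 2⁴ = 16 patterns of (a, b, pH < 7.00, deficit ≥ 12).

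- Intended rule: a and b both met gives 4 patterns. Exactly one of them met gives 2 × 3 = 6, because c holds in 3 of the 4 cord-gas cells. Total 10.
- Signed field, literal coding: 4 + 2 × 2 = 8, because c then holds only in the 2 cells with pH < 7.00.

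The 10 − 8 = 2 lost patterns have pH ≥ 7.00, deficit ≥ 12 and exactly one of a or b. Everything else in the composite still classifies: the death route, a with b, and the pH limb. These are counts of logical patterns, not shares of newborns.

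*If a minus sign was lost from Data Collection.* Reading it as base excess < −12 on the signed scale gives A only, as intended. It then agrees with a deficit of 12 or more except at exactly 12: −12 < −12 is false, while 12 ≥ 12 is true. Secondary outcomes would still be using base excess to mean a positive magnitude, the opposite convention.

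**The case against.** The strongest reply is that the meaning is clinically obvious, that the team includes neonatology expertise, and that criterion c is sound if read as a deficit. On that view the harm needs a signed field and literal coding together, and the documents establish neither. The Data Collection text may also have lost a minus sign when the PDF was read. All of this limits the point. It does not remove it: there is no positive evidence of a lost sign, the Data Collection wording is current text, and restoring the sign leaves two conventions for one term.

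A reader might infer more than the documents support:

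- That the two sections also contradict each other by joining pH and base excess with *or* in one place and *with* in the other. This is not shown. The first is a component of a composite that needs a second criterion and NICU admission; the second is a separately listed item. Such items may differ in strictness.
- That the Data Collection items conflict with Secondary outcomes because they are absent from its list. Neither list claims to be complete, so this is an ambiguity about status only.
- That the asphyxia composite fails. At worst, one limb of one of its three criteria goes inactive.

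**Conclusion.** The point stands as minor. The two directions cannot both be right on one scale, and the Data Collection item is wrong as printed on either: over-inclusive on a signed scale, reversed on a deficit scale. Criterion c is affected only if the field is signed and the rule is coded literally.

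This rests on the assumed target of a deficit of 12 or more and on the printed text being complete. Certainty attaches to the printed inconsistency. A reader might infer that infants have been misclassified or that the neonatal safety comparison is biased. The documents show neither: they give no asphyxia rate, no cord-gas distribution and no description of the stored field, so the effect on event counts cannot be computed. The same rule would apply in both arms, and perinatal death and the separate asphyxia-or-cooling outcome do not use this cut-off as printed. The primary outcome, sample size and primary analysis are unaffected.

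**What to change.** State the base-excess criterion once, on an explicit scale and with a unit, for example base deficit ≥ 12 mmol/L, equivalently base excess ≤ −12 mmol/L. Check that statement against the sign of the stored field before coding, and use the same direction in Secondary outcomes and Data Collection. While editing, confirm whether the Data Collection item combining pH and base excess is a separate outcome or is superseded by the Version 2 asphyxia definition.

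The cost is a wording change in two sections and one look at the stored field. No new data are needed, since cord gases are already listed as available.

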### **Statistical Analysis**

The analysis will be conducted independently by the study statistician (RB). The primary outcome will not be changed during analysis. The trial with an explicit statement of the primary outcome will be registered at clinicaltrials.gov.

The primary analysis will include individual level data from all sites from the baseline period (2015 to 2016) and follow-up thereafter in both arms. The intervention period will be defined separately for each intervention site according to the date of completion of implementation of the program (which varied for the 13 intervention sites from January 31, 2017 to November 30, 2017). Data from the implementation phase (nominally one to two months) will be excluded as a wash-out period. The intervention period ends February 29, 2020 (27 months after completion of site initiation at all intervention sites).

CS rates will be assessed using repeated measures mixed effects logistic regression applied to individual births. We will apply a constrained baseline approach to adjust for pre-intervention data. Explanatory variables (fixed effects) in the model will include time period (in 6 month intervals), and indicators for intervention and post-intervention phases in the intervention sites. The post-intervention

parameter will represent the primary measure of efficacy. Corresponding site-specific random effects will be included for all fixed effects.

Having fewer than 40 sites, a small sample correction will be applied to the standard error for group differences underlying significance tests and confidence interval construction.

If the study has null results it will be important to try and determine if this were due to the ineffectiveness of the guidelines or poor adherence. Therefore, we also plan to assess indicators of guideline uptake such as changes in: duration of labor, time from admission until CS in non-progressing labors and rates of CS for dystocia <6cm.

Descriptive statistics will be used to characterize the labor culture at each site. We will use multiple linear regression to assess the relation between post-intervention percent change in cesarean section rate and site-level sub-scale means in the labor culture survey. In addition, we will examine the association between change in cesarean section rate and adherence to the guidelines for each site by simple linear regression.

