**Methods:** This is a clustered-RCT using a cross forward design. Based on preliminary analysis of Alberta data we have a sufficient number of participating centres to detect a 25% reduction in the risk of CS. The intervention will be designed as an evidence-based, theory-driven program to bring about provider-level behavior change. Physician and nurse barriers and facilitators will be explored using a theory-structured survey. Findings will be mapped to the Capability-Opportunity-Motivation-Behavior Framework (COM-B) and Behavior Change Wheel generating candidate intervention functions. These will guide the literature based identification of appropriate candidate interventions. Candidate strategies will then be assessed using APRAISE (Affordability, Practicability, Effectiveness/Cost Effectiveness, Acceptability, Safety and Equity) and then finalized for physicians and nurses, respectively. We will use a labor culture survey to assess differences in unit culture between intervention sites and to see if those differences may explain any variation in uptake of the recent guidelines.

**Study Team:** The study team includes experts in clinical trials, knowledge translation, intrapartum care, nursing education, neonatology, and health economics. It also includes representatives from two key end user groups, the Alberta Perinatal Health Program and the Alberta Health Services Maternal, Neonatal, Child and Youth Strategic Clinical Network who are providing substantial in kind support.

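### The labor culture survey is meant to explain guideline uptake, but its only planned regression has change in cesarean rate as outcome, and no analysis relates culture to uptake

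*Combined protocol and SAP*

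**What the plan says.** The purpose of the survey is given twice. In the Summary (Methods) it is "to see if those differences may explain any variation in uptake of the recent guidelines"; in Data Collection it is "to see if these differences may explain the variable uptake of the guidelines". The survey goes to physicians and nurses at intervention sites and has six sub-scales.

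Statistical Analysis gives descriptive statistics of culture by site and then one inferential analysis: "We will use multiple linear regression to assess the relation between post-intervention percent change in cesarean section rate and site-level sub-scale means". A second sentence brings in adherence, but not culture: "we will examine the association between change in cesarean section rate and adherence to the guidelines for each site by simple linear regression".

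A site-level measure of uptake is already planned. The implementation outcomes include "guideline adherence (adherence rate by site". Data Collection describes its source: "A random sample of obstetrical charts will be reviewed from the 13 intervention sites", the purpose being "to determine the percentage of cesarean sections for dystocia that were done following the ACOG/SMFM guidelines". On numbers it says "A minimum of 50 charts per site will be reviewed", with all cases taken where a site has fewer.

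Statistical Analysis also says that, after a null result, the team will want to tell an ineffective guideline from poor adherence. It lists other uptake indicators for this: labor duration, time from admission to CS, and CS for dystocia below 6 cm.

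**The concern.** The question concerns uptake, and the outcome analyzed is CS change. The plan itself treats these as different things: it lists adherence as its own implementation outcome and wants to separate poor adherence from an ineffective guideline.

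A site's change in CS rate reflects how far the guideline was taken up, multiplied by what the guideline does to CS, plus sampling noise. If the second factor is small, culture could largely determine which sites adopted the guideline and the regression would show nothing. In the other direction, an association would not establish a link with uptake. Sub-scales such as cesarean safety or fear of vaginal birth could be related to CS rates by routes other than the guideline.

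At stake is whether the survey answers the question for which it was added. The primary estimate and the safety outcomes are not affected.

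**Working it through.** **1. The texts side by side.** The plan gives no sample size or power for the survey regression, so there is no stated figure to reproduce. The links it specifies are:

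| Link | Planned analysis |
|---|---|
| Culture and CS change | Multiple linear regression |
| Adherence and CS change | Simple linear regression |
| Culture and adherence (the stated aim) | None |

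The survey also asks about engagement with the guidelines, but no analysis beyond description is given for those items.

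**2. Why CS change is a poor substitute.** For site s, let u be uptake, R the relative cut in CS at full uptake, and e the sampling error. Then percent change = -100·R·u + e. If culture acts on CS only through uptake, its covariance with percent change is -100·R·Cov(culture, u). At R = 0 this is zero, however strongly culture drives uptake. This result needs no assumed figure.

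**3. Size when R is not zero.** From the documents: 13 sites, six sub-scales, at least 50 charts per site where available, 2-year baseline, 27 months of follow-up, baseline CS 32%, target reduction 25%, and a floor of 70 primiparous births a year. Assumed: uptake mean 50% and SD 20 points between sites, culture-uptake correlation 0.7, volumes of 70 to 2,000 births a year, chart adherence an unbiased reading of u, and 50 charts at every site.

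Signal in percent change at R = 0.25: SD = 0.25 × 20 = 5 points.

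Noise, by the delta method with CS going from 32% to 28%: SE = 100 × (0.28/0.32) × √[0.68/(0.32·n0) + 0.72/(0.28·n1)].
- 70 births a year (n0 = 140, n1 = 157.5): 87.5 × √(0.01518 + 0.01633) = 15.5 points.
- 1,000 births a year (n0 = 2,000, n1 = 2,250): 87.5 × √(0.00106 + 0.00114) = 4.1 points.

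Implied correlation of culture with percent change, if all sites were of that size:
- 70 a year: 0.7 × 5/√(5² + 15.5²) = 0.21.
- 1,000 a year: 0.7 × 5/√(5² + 4.1²) = 0.54.

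For chart adherence, sampling variance = (0.5 × 0.5 - 0.2²)/50 = 0.0042, an SD of 6.5 points. The correlation is 0.7 × 20/√(20² + 6.5²) = 0.67.

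**4. Power by simulation, same assumptions, two-sided 5%.** In the six-predictor model, one sub-scale drives uptake and five are noise.

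| Outcome | CS cut at full uptake | One predictor | Six predictors |
|---|---|---|---|
| Chart adherence | any (0 to 25%) | 75% | 48% |
| CS change | none | 5% | 5% |
| CS change | 10% | 8% | not tabulated |
| CS change | 25% | 20% to 25% | about 15% |

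The 20% to 25% spread comes from how site volumes are spread over 70 to 2,000. A uniform 350 births a year gives 29%.

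**5. Sensitivity.** A second six-predictor simulation assumed about 700 baseline and 800 follow-up births per site, with mean CS reductions of 0, 5%, 10% and 25%. At a culture-uptake correlation of 0.8, power with CS change was 5%, 6%, 11% and 37%, against 66% to 68% with adherence. At 0.6 it was 5%, 6%, 8% and 20%, against 33% to 34%.

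**6. Degrees of freedom.** With six sub-scales, 13 - 6 - 1 = 6 residual degrees of freedom remain. With one, 13 - 1 - 1 = 11. This limit applies to either outcome.

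**The case against.** **CS change is a usable proxy.** In part. If the guideline works and CS falls in step with uptake, the planned regression has some power. A reader might infer that it cannot answer the question at all; that is too strong. It cannot answer it directly.

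**The null case is already covered.** Largely true for the trial as a whole. The plan has separate uptake indicators and a regression of CS change on adherence. A reader might infer that the trial cannot tell poor adherence from an ineffective guideline. The documents do not support that. Only the culture-uptake link is missing.

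**No one says the result will be misread.** Correct. The plan describes the regression accurately as a relation with CS change. It nowhere says that a null finding will be taken to mean that culture does not explain uptake. That misreading is a risk, not a plan.

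**Chart adherence is imperfect.** This stands. It covers only births that ended in CS for dystocia, starts in December 2017 with no baseline, and rests on fewer than 50 charts where cases are few. The simulated power treats it as equal to uptake and is therefore favorable to it.

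**Change in CS below 6 cm would be a better lead outcome.** A reader might infer this and attach the 75% to it. That figure belongs to chart adherence with one predictor. The documents give no rate of CS below 6 cm. With an assumed baseline of 5% to 12% and a cut of 25% to 80% at full uptake, power was about 7% to 46% with one predictor and 6% to 27% with six. It is itself a change in a CS rate with fewer events, so it suits a supporting role.

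**Conclusion.** The mismatch holds, and nothing elsewhere in the document cures it: the survey's stated question has no analysis, and its one regression addresses a different question. That regression carries no information about uptake through CS if the guideline does not lower CS; this follows from the structure alone. The remaining figures depend on the assumed spread of uptake, correlation and site volumes. Under the main set, power is about 75% (one predictor) or 48% (six) with adherence as outcome, against about 15% to 25% with CS change at a 25% full-uptake effect. These illustrate the ordering and do not predict what this trial would find.

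The point is minor. It concerns an exploratory analysis of 13 sites and leaves the primary result, the secondary outcomes and the safety assessment untouched.

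**What to change.** In Statistical Analysis, add a regression of site-level chart-review adherence on the culture sub-scale means and label it exploratory. Enter sub-scales one at a time, or name a few in advance. Report the number of charts behind each site's adherence figure and state that the measure covers only CS for dystocia after implementation.

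Use the uptake indicators already listed, such as change in CS for dystocia below 6 cm, as supporting outcomes. Keep the CS-change regression under its own label, as an analysis of culture and change in CS rate, and state that no conclusion about uptake will be drawn from it.

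The cost is small. The plan already provides for the data at the same sites, and the price is one more low-power exploratory result to report.
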